All statistical analyses will be conducted using IBM SPSS Statistics version 28.0 (IBM Corp., Armonk, NY, USA). Statistical significance will be set at a two-sided $p < 0.05$. Continuous variables will be presented as mean and standard deviation (SD) or median and interquartile range (IQR) where appropriate, while categorical variables will be summarized as frequencies and percentages.

Analyses will follow the intention-to-treat (ITT) principle, including all participants as randomized regardless of protocol adherence. A per-protocol analysis may also be conducted as a sensitivity analysis.

Study Design Considerations (Crossover Structure)

This study adopts a two-period, two-sequence crossover randomized controlled design:

Sequence A: VR CAVE → Simulated Home

Sequence B: Simulated Home → VR CAVE

Each participant serves as their own control, improving statistical efficiency and reducing between-subject variability.

Key effects to be evaluated include:

Intervention (VR CAVE vs simulated home)

Period effect (first vs second session)

Sequence effect (order of intervention)

Carryover effect (residual effect from first intervention)

Outcome Measures

Primary outcomes:

Clinical competence (CCQ total and subscale scores)

Self-confidence and satisfaction (SSS scores)

Cultural competence (CCA total and subscale scores)

All outcomes are treated as continuous variables.

Baseline Analysis

Baseline characteristics (e.g., gender, prior clinical experience) will be compared between the two randomized sequences:

Categorical variables: Chi-square test or Fisher's exact test

Continuous variables: Independent samples t-test or Mann-Whitney U test (if non-normal)

This step assesses the success of randomization.

Primary Analysis

A linear mixed-effects model (LMM) will be used to evaluate intervention effects while accounting for repeated measures and crossover design.

Model specification:

Random effect: Participant ID

Fixed effects:

Intervention (VR CAVE vs simulated home)

Period (1 vs 2)

Sequence (A vs B)

Time (pre vs post)

Interaction terms (e.g., intervention \times time)

The primary parameter of interest is the intervention effect, estimated as the difference in outcome scores between VR CAVE and simulated home conditions.

Carryover Effect Assessment

To assess potential carryover effects:

A sequence effect will first be examined within the mixed model.

Additionally, an interaction term (intervention \times period) may be explored.

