The principal investigator will conduct a separate briefing session before the intervention at a mutually convenient time. This session will ensure that they understand all logistics and the knowledge required to guide the students through the cases in the study.

All participants will have a pre briefing time before the start of scenario. The principal investigator will explain the nature, purpose, procedures, risks and benefits of the proposed project to potential participants. Confidentiality and the voluntary nature of participation will be emphasized. Students who agree to participate will sign a consent form. The principal investigator will provide briefings on the project logistics and student expectations to ensure they are fully informed.

Then, students will be asked to take a pre-test and post-test on knowledge, self-confidence, satisfaction, and cultural competence in community health nursing.

Phase 3: Implementing the VR CAVE model

In the second semester, the VR CAVE model will be applied with Year 5 nursing students in the Community & Global Health Nursing (NURS4604) course. Students will form groups and actively participate in conducting home assessments and identifying health hazards for the patient with a play time of 20 minutes. In the proposed study, fifth-year nursing students will interact with a VR CAVE, a virtual reality environment designed to simulate home visits for two unique patients, Stone Wong and May Wong, both situated in a poverty-stricken home setting (Figure 1). With around twenty hidden cues in each case, the VR CAVE provides a realistic and immersive environment that mirrors the patients' homes. These cues symbolize potential health risks and cultural preferences related to health, thus challenging the students to observe, assess, and respond effectively.

Prior to the intervention, an online Qualtrics e-consent will be obtained from the participants. Furthermore, a pre-test will be conducted using the Clinical Competence Questionnaire (CCQ), Student Satisfaction and Self-confidence in Learning (SSS), and Cultural Competence Assessment Instrument (CCA). This will allow us to measure the baseline competencies of the students before the intervention.

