The intervention group will then undergo the VR CAVE experience in Lab 1, while the control group will conduct a simulated home visit in the same lab. After completing the simulated home visit, the students will take an online Qualtrics post-test on the CCQ, CCA, and SSS. This will provide us with data to compare the competencies of the students post-intervention, and to assess the effectiveness of the VR CAVE as a training tool for nursing students.

Following the initial lab session, the two groups will switch settings for the second lab, thus ensuring a comprehensive and balanced assessment of the effects of the VR CAVE intervention.

The intervention group that initially experienced the VR CAVE will now shift to the

conventional simulated home, while the control group will have the opportunity to experience the VR CAVE intervention. This crossover design will provide a holistic view of the students' learning experience in both simulated environments.

Before the second lab session, participants will once again provide e-consent using Qualtrics. This reaffirms the ongoing voluntary nature of their participation. As in the first lab session, students will complete pre-tests using the Clinical Competence Questionnaire (CCQ), Student Satisfaction and Self-confidence in Learning (SSS), and Cultural Competence Assessment Instrument (CCA). This will allow us to monitor any changes in competencies as a result of the initial lab session.

After completing the second lab session, students will perform the same set of post-tests online via Qualtrics based on the CCQ, CCA, and SSS. This will enable us to evaluate any shifts in clinical, cultural, and satisfaction competencies following exposure to both the VR CAVE and the conventional simulated home. This comprehensive testing strategy will ensure that we capture a wide range of data to assess the overall effectiveness and impact of the VR CAVE technology in nursing education. The flow chart is shown in Figure 2.

Figure 1 VR CAVE model for poverty home

[figure not shown]

Figure 2 Flowchart of the study

Phase 4: Data analysis and generating design principles for a VR CAVE model

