Appendix 2 Student satisfaction and Self-confidence in Learning (SSS)

Student Satisfaction and Self-Confidence in Learning

Instructions: This questionnaire is a series of statements about your personal attitudes about the instruction you receive during your simulation activity. Each item represents a statement about your attitude toward your satisfaction with learning and self-confidence in obtaining the instruction you need. There are no right or wrong answers. You will probably agree with some of the statements and disagree with others. Please indicate your own personal feelings about each statement below by marking the numbers that best describe your attitude or beliefs. Please be truthful and describe your attitude as it really is, not what you would like for it to be. This is anonymous with the results being compiled as a group, not individually.

Mark:

- 1 = STRONGLY DISAGREE with the statement
- 2 = DISAGREE with the statement
- 3 = UNDECIDED - you neither agree or disagree with the statement
- 4 = AGREE with the statement
- 5 = STRONGLY AGREE with the statement

Satisfaction with Current Learning	SD	D	UN	A	SA
1. The teaching methods used in this simulation were helpful and effective.	 1	 2	 3	 4	 5
2. The simulation provided me with a variety of learning materials and activities to promote my learning the medical surgical curriculum.	 1	 2	 3	 4	 5
3. I enjoyed how my instructor taught the simulation.	 1	 2	 3	 4	 5
4. The teaching materials used in this simulation were motivating and helped me to learn.	 1	 2	 3	 4	 5
5. The way my instructor(s) taught the simulation was suitable to the way I learn.	 1	 2	 3	 4	 5
Self-confidence in Learning	SD	D	UN	A	SA
6. I am confident that I am mastering the content of the simulation activity that my instructors presented to me.	 1	 2	 3	 4	 5

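### The SSS mostly rates a simulation already experienced but is also given before each lab; using those pre-test rows can distort the size of the satisfaction and self-confidence effect

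*Combined protocol and SAP*

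**What the plan says.** The SAP (Outcome Measures) lists "Self-confidence and satisfaction (SSS scores" among the primary outcomes, beside the CCQ and CCA. Appendix 2 describes the SSS as "statements about your personal attitudes about the instruction you receive during your simulation activity". Satisfaction item 1 reads "The teaching methods used in this simulation were helpful and effective", and self-confidence item 6 reads "I am confident that I am mastering the content of the simulation activity that my instructors presented to me".

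Phase 3 gives the SSS four times:

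- **Before Lab 1:** "a pre-test will be conducted using the Clinical Competence Questionnaire (CCQ), Student Satisfaction and Self-confidence in Learning (SSS", together with the CCA. The stated purpose is: "This will allow us to measure the baseline competencies of the students before the intervention".
- **After Lab 1:** post-test.
- **Before Lab 2, when the groups swap settings:** "As in the first lab session, students will complete pre-tests using the Clinical Competence Questionnaire (CCQ), Student Satisfaction and Self-confidence in Learning (SSS". The purpose given is to track change arising from the first lab.
- **After Lab 2:** post-test.

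The SAP's Primary Analysis is a mixed model with participant as random effect and with intervention, period, sequence, time (pre or post) and interactions as fixed effects. Intervention × time is the interaction it names as an example. The primary parameter is called the intervention effect, but it is not tied to a model term. Phase 4 applies a group × time model to the SSS by name, and the SAP adds paired pre-post tests within each condition. The carryover assessment looks first at the sequence effect; a significant result confines the analysis to period 1. Nothing in the documents rewords the SSS for use before a simulation, limits it to the post-test, or leaves its pre-test rows out of the analysis.

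**The concern.** A pre-test serves as a baseline only if the question means the same thing before and after. The CCQ and CCA do not refer to a particular simulation, so they can be answered beforehand. SSS items 1 to 9 clearly refer to teaching, content or resources in a given simulation; items 10 to 13 do so less.

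Before Lab 1 there is no study simulation to rate. Before Lab 2 the only one to rate is the other condition. A student about to enter the simulated home may therefore be rating the VR CAVE, yet the row is coded as simulated home, pre. The reverse holds in the other sequence.

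At stake are the size of the SSS effect, its confidence interval and standardised effect, power if the pooled main effect is read, and the carryover decision.

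**Working it through.** The documents give no effect size, SD or power calculation, so there is no stated figure to reproduce. The check derives the expected cell means under the SAP's list of model terms.

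**Inputs**

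- V and H: mean post-test SSS after VR CAVE and simulated home; D = V − H.
- b: mean Lab 1 pre-test score, with no study simulation to refer to.
- w: share of the Lab 2 pre-test answer that rates Lab 1. This is an assumption, taken over its whole range from 0 to 1.
- Equal sequences, complete data and no true carryover (assumptions). A shift common to both sequences within a lab cancels.

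**Cell means**

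| Sequence | Lab 1 pre | Lab 1 post | Lab 2 pre | Lab 2 post |
|---|---|---|---|---|
| A (VR, then home) | b | V | (1−w)b + wV | H |
| B (home, then VR) | b | H | (1−w)b + wH | V |

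**Intervention × time** (VR minus home difference in pre-post change)

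- Lab 1: (V − b) − (H − b) = D. The baseline b cancels.
- Lab 2: [V − (1−w)b − wH] − [H − (1−w)b − wV] = D + wD.
- Average: D(1 + w/2).

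**Intervention main effect, pre and post rows pooled**

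- Lab 1: (b + V)/2 − (b + H)/2 = D/2.
- Lab 2: (D − wD)/2.
- Average: D(1/2 − w/4).

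**Sequence effect** (A minus B, over four rows)

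- [(V + wV + H) − (H + wH + V)]/4 = wD/4.

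**Post-test scores only**

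- Intervention: V − H = D in each lab, for any w.
- Sequence: (V + H)/2 − (H + V)/2 = 0.

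| w | Intervention × time | Pooled main effect | Sequence effect | Post-test only |
|---|---|---|---|---|
| 0 | 1.00D | 0.50D | 0 | D |
| 0.5 | 1.25D | 0.375D | 0.125D | D |
| 1 | 1.50D | 0.25D | 0.25D | D |

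**Within-condition tests.** Take assumed item means V = 4.3, H = 4.0, b = 3.0 and w = 1. The VR change is 4.3 − 3.0 = 1.3 in Lab 1 and 4.3 − 4.0 = 0.3 in Lab 2. The home change is 4.0 − 3.0 = 1.0 in Lab 1 and 4.0 − 4.3 = −0.3 in Lab 2. The Lab 1 changes depend on b, which has no referent. The Lab 2 changes are just the between-arm difference with a sign attached. The averages are 0.80 and 0.35; their difference is 0.45 = 1.5 × 0.3, in agreement with the formula.

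**Simulated mixed model.** Assumptions: 220 students (the number invited), equal sequences, SD 1, within-person correlation 0.5, D = 0.50, 120 runs.

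| | w = 0 | w = 1 |
|---|---|---|
| Intervention × time | 0.497 | 0.747 |
| Pooled main effect | 0.252 | 0.127 |
| Sequence effect | −0.006 | 0.119 |
| Sequence test p < 0.05 | 3.3% of runs | 19.2% of runs |
| Post-test contrast | 0.501 | 0.501 |

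With D = 0, the mean intervention × time and main-effect estimates were −0.003 and 0.002 at both values of w.

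**The case against.** Several objections stand and limit the point.

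- **A reader might infer that the planned model necessarily gives a wrong SSS effect.** The documents do not go that far. The SAP describes the primary parameter only as a difference in scores between conditions, and a post-test contrast taken from the same model would return D. The difficulty is that no such contrast is specified, so the plan equally allows the interaction or the pooled main effect to be reported.
- **A reader might take 50% too large and 75% too small as the size of the error.** Those are the values at w = 1. How students would answer the Lab 2 pre-test is inferred from the item wording and from the purpose Phase 3 gives for that pre-test. At w = 0 the interaction is correct.
- **Half of D is lost from the main effect for another reason.** Pooling pre with post rows gives 0.5D at w = 0 whatever the instrument, so it would affect the CCQ and CCA as well. The SSS timing accounts only for the further step from 0.5D towards 0.25D.
- **The Lab 1 pre-test might seem to bias the comparison of arms.** Under randomisation b cancels. It adds noise and spoils the within-condition tests, and no more.
- **The pre-test is not wholly without meaning.** Items 10 to 13, on responsibility for learning, getting help and using simulation activities, can largely be answered beforehand. Items 1 to 9 cannot, and the scores combine the two kinds.
- **A false VR benefit might be feared.** With D = 0 there is no bias, and the sign of neither estimate changes for any w from 0 to 1.

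What remains is that a primary outcome has pre-test rows of unclear or wrong reference, a model that uses them, and no stated term to report.

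**Conclusion.** The point holds in a conditional form. The mismatch between the SSS items and their timing is plain in the documents; the size of the distortion depends on w. Depending on which term is read, the reported SSS effect is 1.0D to 1.5D or 0.5D to 0.25D, and only the second halving of the main effect is due to the SSS. For any w above 0 and D not zero, a sequence effect of wD/4 arises without carryover. It can set off the first-period-only rule and discard the second lab; the simulated 19% against 3% depends on the assumed effect, SD, correlation and sample size. The multiples of D do not depend on SD or correlation when sequences are equal and data complete.

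The harm is to effect size, confidence interval, power and the carryover decision. The documents do not support a claim of false-positive VR effects. The planned pre-post SSS tests within each condition are not interpretable at any w, because b has no study simulation behind it.

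**What to change.** For the SSS, state in the SAP and in Phase 4 that:

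- the analysis uses only the two post-test scores per student, in a mixed model with intervention, period and sequence as fixed effects and participant as random effect, and the intervention coefficient is the SSS effect;
- the SSS is removed from the time and intervention × time terms and from the paired pre-post tests;
- any SSS pre-test data already collected are excluded from the model.

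This gives D for every w and removes the artificial sequence effect. Dropping the SSS from the two pre-test surveys is sensible and shortens each by 13 items, but it is optional, since the analysis wording alone removes the distortion. The CCQ and CCA can keep their pre-tests.

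The cost is a change of wording. No pre-post SSS change would be reported, but that change is not interpretable as planned.

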The primary and secondary analyses will involve descriptive statistics, including mean and standard deviation, to summarize participants' demographics and scores from the Clinical Competence Questionnaire (CCQ), Cultural Competence Health Practitioner Assessment (CCHPA-129), and Student Satisfaction and Self-Confidence in Learning (SSS). Baseline characteristics of the intervention and control groups will be compared using the χ^2 test or Fisher's exact test for categorical data and the independent t-test for continuous data. The CCQ, CCHPA-129, and SSS scores will be evaluated using a linear mixed-model analysis. Participants will be included as the random effect with time, group, randomization sequence order, and group x time interaction as fixed effects. The analysis will adhere to the intention-to-treat principle,

conducted on subjects as randomized. All statistical analyses will be performed using IBM SPSS version 28.0. All statistical tests will be two-sided with the level of significance set at 0.05.

Design principles specific to the context of the VR CAVE will be generated based on the findings of this project. These design principles will guide and be applied in further designing and developing VR CAVE for community health nursing.

Project schedule

Phase	Estimated Completion Time
1: Preparatory phase	January 2025
2: Briefing session	February 2025
3: Implementing the VR CAVE model	April-August2025
4: Data analysis and generating design principles for a VR CAVE model phase	January 2026

Reference

1. Thompson, C. W., Moscola, S., & Buckland, S. T. (2021). Nursing student perceptions of home visit simulation scenarios. *Nursing education perspectives*, 42(2), 113-114.
3. Alıcı, N. K., & Emiroğlu, O. N. (2020). Students' home visit experiences within the scope of public health nursing course: A qualitative study. *Acıbadem Üniversitesi Sağlık Bilimleri Dergisi*, 12(1), 146-151.
4. Dalton, J. M., Aber, C., & Fawcett, J. (2009). Students' perceptions of home visiting. *Home Healthcare Now*, 27(4), 253-261.
5. Meeley, N. G. (2021). Undergraduate student nurses' experiences of their community placements. *Nurse Education Today*, 106, 105054.

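### The SAP and the protocol's Phase 4 section state different mixed models and nothing says which governs; the Phase 4 model omits period and leaves *group* and *time* undefined

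*Combined protocol and SAP*

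**What the plan says.** The SAP section (Study Design Considerations and Primary Analysis) describes two sequences, A and B, over two periods. Its linear mixed model has a random participant effect and fixed effects for intervention, period, sequence and time, where time has two levels, pre and post. Interactions are added, with intervention x time given as an example. The named target is the difference between the VR CAVE and simulated-home conditions.

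The protocol's Phase 4 section also covers the primary and secondary analyses. It specifies a mixed model with a participant random effect and "time, group, randomization sequence order, and group x time interaction as fixed effects". It has no period term, no intervention term and no stated levels for time. (It also names a different cultural-competence instrument from the SAP, which is a separate matter.)

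The protocol's use of *group* bears on how that model is read. In Phase 3, the arm that starts in VR keeps its name at the switch: "The intervention group that initially experienced the VR CAVE will now shift to the" other setting. The second arm likewise keeps its name in Lab 2, when it moves into VR: "while the control group will have the opportunity to experience the VR CAVE intervention". The labels stay with the students and do not follow the condition. Phase 4 keeps that usage: "Baseline characteristics of the intervention and control groups will be compared using the" usual two-sample tests. The SAP describes the same baseline comparison as one between the randomized sequences.

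**The concern.** An analyst could follow either section and claim to have followed the plan. The SAP model is built for a crossover. The Phase 4 model is not clearly so, and what it tests depends on two things it leaves open: what *group* is, and how many levels *time* has.

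Depending on the answers, the Phase 4 group x time test carries no information on the VR effect, or estimates it with avoidable loss of precision, or becomes an omnibus test that does not return the single VR-minus-home difference the SAP targets. If this is left open, the choice of primary model can be made after the outcome data are seen.

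**Working it through.** The documents give no effect size, SD, correlation or power figure, so there is nothing to reproduce.

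**Inputs from the documents.** Two sequences, two labs, a pre-test and post-test in each lab (Phase 3), two-sided 5% tests, and 220 students invited, which is an upper bound on the number analysed.

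**Assumptions for illustration.** Total SD 1; gain with simulated home g = 1.0; extra VR gain d = 0.3; additive lab shift 0.5; intraclass correlation 0.5 or 0.7; Lab 1 gains either lost or fully retained by Lab 2; 110 students per sequence.

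**Reading 1: group = starting arm, time = pre/post.**
- The columns intercept, time, group, sequence and group x time number 5 and have rank 4, because group and sequence are the same variable.
- Arm A gains g + d in Lab 1 and g in Lab 2, a mean of g + d/2. Arm B gains g and then g + d, a mean of g + d/2. The expected group x time contrast is (g + d/2) − (g + d/2) = 0.
- This needs no SD, correlation or retention value. It needs only that d is the same in both labs. If the VR effect were d1 in Lab 1 and d2 in Lab 2, the contrast would be (d1 − d2)/2, which is still not the VR effect.
- In simulation with d = 0.3, the test rejected in 0–2.5% of runs.

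**Reading 2: group = condition received, time = pre/post, period omitted.**
- The interaction averages each student's VR gain minus home gain. A lab shift common to pre and post cancels, so the expected estimate is 0.300 at 110/110, 120/100 and 130/90.
- The shift is not modelled, so it enters the residual. The variance of the contrast is 4σ²/N, with σ² = 1 − correlation. An average shift s between labs raises the estimated residual variance to about σ² + s²/3.
- Correlation 0.5, period included: SE = √(4 × 0.5/220) = 0.095.
- No retention, s = 0.5: 0.5 + 0.083 = 0.583, reported SE = 0.103.
- Full retention, s = 0.5 + 1.15 (the mean gain) = 1.65: 0.5 + 0.908 = 1.408, reported SE = 0.160.

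Simulated rejection rates at d = 0.3, 110 per sequence, over correlations 0.5 and 0.7:

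| Model | No retention | Full retention |
|---|---|---|
| Condition x time, period omitted | 86–98% | 45–56% |
| Condition x time, period included | 89–98% | 88–99% |

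With no true effect, the period-omitted test rejected in 0–3% of runs, so it is conservative, not anti-conservative.

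**Reading 3: group = starting arm, time = four occasions.**
- Period is contained in time. The expected A − B differences are 0, 0.3, 0, −0.3 with no retention, and 0, 0.3, 0.3, 0 with full retention.
- The 3-df group x time test rejected in 75–100% of runs. The effect is detected, but the test does not give one VR-minus-home estimate.

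**A limit of the SAP model too.** Suppose the gain itself differs by δ in Lab 2. Without a period x time term, condition x time has expectation d + δ(nB − nA)/N, whether or not the Period main effect is present. With δ = −0.5:
- 120/100: 0.3 + 0.5 × 20/220 = 0.345
- 130/90: 0.3 + 0.5 × 40/220 = 0.391

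With period x time in the model, the two sequences estimate d − δ and d + δ. Their equally weighted mean is d = 0.300.

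**The case against.** The strongest reply is that the Phase 4 author meant the condition received. Sequence order is listed separately beside group, and no one would knowingly enter the same variable twice. On that view the Phase 4 model is the SAP model less the period term. The SAP section is also the more detailed one, carries the title, and already holds a workable model with the right target.

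Much of this stands. *Group* is used for the starting arm but not defined, and the separate sequence term does point the other way. The zero expectation also needs two-level time, which Phase 4 does not state. Phase 3 describes four test occasions, and under four-level time the effect is not missed. The rank deficiency alone would not spoil the interaction test, since software drops the redundant column.

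A reader might infer that the trial has no valid test of VR CAVE. The documents do not support that, because the SAP model supplies one. A reader might also infer that leaving out period biases the VR estimate when the sequences are unequal. For condition x time under an additive lab shift it does not. Such a shift would bias the condition main effect, which is a different coefficient.

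What the reply does not remove is that two models stand in one document without precedence, and that one of them cannot be fitted without guessing two definitions.

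**Conclusion.** The point holds as a conflict between two model statements, one of them ambiguous, and it should be corrected before analysis. It does not show that the trial lacks a usable primary analysis.

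The consequence of following Phase 4 depends on the reading. The zero expectation under starting arm and pre/post time is algebra and rests only on a VR effect that is equal in both labs. The loss of power under condition received is illustrative: it ranges from slight to about half, according to the assumed lab-to-lab shift, and also depends on the assumed effect, correlation and 110 students per sequence. The four-occasion reading loses the single estimate, not the ability to detect an effect.

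**What to change.** In the Phase 4 section, replace the model sentence with a reference to the SAP's Primary Analysis. In the SAP:

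- define the factor as the condition received in that lab, VR CAVE or simulated home, and do not use *group* for it;
- keep Period and Sequence as fixed effects;
- state that time is pre or post within each lab;
- name condition x time as the primary contrast, since intervention x time is at present only an example;
- add period x time, so that a difference in gain between labs does not bias that contrast when the sequences are unequal.

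The cost is wording only: no change to data collection, instruments or sample. The change should be dated and made before outcome data are examined. If they have been examined already, the report should say so.
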